and total cumulative opioid and benzodiazepine doses have been associated with an increased risk of IWS (4, 5, 14, 15). The onset of withdrawal symptoms can occur within 12 hours following opioid discontinuation and may be precipitated by an abrupt taper or the administration of opioid antagonists (1, 18).

Clinical presentation

Most literature is extracted from PICU studies designed with the objective of developing or validating IWS assessment tools (16). Ista et al. compiled a list of 26 symptoms of mixed withdrawal as reported in the literature and evaluated the co-occurrence of IWS symptoms in low and high risk patients (19). An expert panel identified 15 symptoms encompassing the central nervous system (anxiety, agitation, inconsolable crying, grimacing, sleep disturbance, hallucinations), autonomic dysfunction (increased muscle tension, muscle twitching, tremors, tachycardia, tachypnea, fever, sweating) and gastrointestinal problems (vomiting, diarrhea) (19, 20). However, the investigators did not control for potential confounders of IWS diagnosis such as inadequate pain management or delirium. A review by Chiu et al. identified symptoms of opioid withdrawal specific to the neonatal and PICU populations such as inconsolable crying, irritability, grimacing, tremors, increased muscle tone, poor feeding, vomiting, diarrhea, sleep disturbance, hyperactive Moro reflex, fever, nasal stuffiness, sweating and yawning (4). However, evaluation of symptoms and outcomes were done by the same practitioner in select studies, which may have confounded the results (4, 21).

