Once the patient begins the targeted opioid weaning of $\geq 10\%$, investigators will perform evaluations daily between 10am and 2pm. These evaluations will consist of using pre-tested data collection sheets to record signs and symptoms of possible OIWS, opioid doses, administered medications, laboratory values and other clinical data such as the RASS, CPOT and CAM-ICU scores. Data collection will be based on subject observation and interview when possible, nurse assessments, medical charts and laboratory results. Serum cortisol levels will be measured on the first day of opioid weaning (± 2 hours from dose decrease) and on the day patient is transferred to the ward or 72 hours from start of weaning whichever occurs first.

Once a weaning episode is identified, the physician collaborator will be contacted to perform daily DSM-5 evaluations. DSM-5 evaluations will be placed in opaque envelopes and investigators will be blinded to the results throughout the study. Additionally, for each patient, at least one inter-rater DSM-5 evaluation between 2 physician collaborators will be performed in order to assess interrater reliability. The two evaluations will be done within 2 hours of each other to minimize time-related discrepancies.

If opioid weaning is unsuccessful and opioid dose is re-increased, the subject will continue to be observed, however daily evaluations will only resume at the next weaning episode. Daily follow-up ends on day of transfer to the ward. One additional data collection and DSM-5 evaluation will be performed on the same day within 24 to 96 hours following transfer. Follow up ends 14 days after initial opioid weaning if patient remains in the ICU or if patient dies.

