5.1 Statistical analysis

5.1.1 Descriptive statistics

Demographic and clinical characteristics of patients who developed OIWS will be compared to those who did not. Categorical variables will be presented as proportions. For continuous variables, means and standard deviations will be computed for normal distributions whereas medians (interquartile range) will be used for non-normal distributions.

For the primary outcome, episodes will be compared between the withdrawal positive (W+) group and the withdrawal negative (W-) group. Every day on which the DSM-5 is positive is equivalent to an episode of withdrawal, whereas a negative DSM-5 counts as an episode in which no withdrawal was observed. Patients who are positive for at least one episode of withdrawal make up the W+ group, whereas those who did not have a single episode of withdrawal make up the W- group, thus eliminating crossover. If a single patient experiences multiple days of withdrawal, s/he will account for multiple episodes in the study. Signs and symptoms will be tallied per episode and compared between the two groups. The results will be presented as proportions (i.e. incidence of symptom per total episodes). In the event of a discordant inter-rater evaluation, only the positive result will be taken into account.

For the secondary outcome, serum cortisol levels and changes in serum cortisol levels are continuous variables and therefore descriptive statistics will be used as stated above, depending on the distribution.

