Dermatologic symptoms	Mottling	Presence of violaceous marbled discoloration of the skin during evaluation or according to nurse assessment in the previous 24h	Qualitative nominal (dichotomous)
	Piloerection	Presence during evaluation or according to nurse assessment in the previous 24h	Qualitative nominal (dichotomous)
	Sweating	Presence without apparent reason (not caused by room temperature) during evaluation or according to nurse assessment in the previous 24h	Qualitative nominal (dichotomous)
Musculoskeletal symptoms	Bone, joint or muscle aches	Presence during evaluation or according to nurse assessment in the previous 24h	Qualitative nominal (dichotomous)
	Muscle cramps	Presence during evaluation or according to nurse assessment in the previous 24h	Qualitative nominal (dichotomous)
	Muscle tone	Presence during evaluation or according to nurse assessment in the previous 24h	Qualitative nominal (dichotomous)

		(e.g. clenching wrists and toes, hunched shoulders, abnormal tense position of head, arm or legs)	
	Uncoordinated/ repetitive movement	Presence of involuntary movements of arm and/or legs, muscle twitches, during evaluation or according to nurse assessment in the previous 24h	Qualitative nominal (dichotomous)

^a Previous 24h designate the interval between midnight of the previous day and midnight of the day on which evaluation of the signs and symptoms occurs. A fixed time frame was chosen to standardize collection of signs and symptoms.

^b Nurse assessment comprises written (i.e. notes in medical chart or patient flow sheet) and/or verbal communication.

^c On the day of transfer, patients will be evaluated from midnight of the previous day until time of evaluation. Following transfer to ward, patients will be evaluated from midnight of the current day to time of evaluation.

Appendix IV. Diagnostic and Statistical Manual of Mental Diagnosis-V (DSM-5): “Opioid Withdrawal” criteria.

Diagnostic criteria:

A. Presence of either of the following;

1. Cessation of (or reduction in) opioid use that has been heavy and prolonged (i.e., several weeks or longer).
2. Administration of an opioid antagonist after a period of opioid use.

B. Three (or more) of the following developing within minutes to several days after

1. Dysphoric mood.
2. Nausea or vomiting.
3. Muscle aches.
4. Lacrimation or rhinorrhea.
5. Pupillary dilation, piloerection, or sweating.
6. Yawning.
7. Fever.
8. Insomnia.

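### At ordinary ICU visits, 14 of the 30 signs are charted from the calendar day before the DSM-5 label, and on the first sheet that chart window can lie wholly before the wean

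*Combined protocol and SAP*

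**What the plan says.** Once a wean of at least 10% has begun, section 4.5 states that "investigators will perform evaluations daily between 10am and 2pm". Many Appendix III signs are scored over a previous-24-hour period, which footnote a defines: "Previous 24h designate the interval between midnight of the previous day and midnight of the day on which evaluation of the signs and symptoms occurs". The reason it gives for the fixed frame is standardized collection.

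Footnote c makes two exceptions. For the transfer day: "On the day of transfer, patients will be evaluated from midnight of the previous day until time of evaluation". For the ward visit: "Following transfer to ward, patients will be evaluated from midnight of the current day to time of evaluation".

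For the diagnosis, section 4.5 says that "the physician collaborator will be contacted to perform daily DSM-5 evaluations". It gives neither a clock time nor a look-back period for that rating. Section 5.1.1 then attaches the label to the calendar day: "Every day on which the DSM-5 is positive is equivalent to an episode of withdrawal". The primary output follows from that: "Signs and symptoms will be tallied per episode and compared between the two groups". Section 4.4.1 defines the dependent variable as signs from the investigator's daily evaluation once weaning has started.

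**The concern.** The sign window and the diagnostic label refer to different days. At an ordinary ICU visit on day D, chart-sourced signs come from day D-1, but the episode is labelled by the DSM-5 rating of day D. A physician could count fever towards a positive rating on day D while the paired sheet reports the highest temperature of day D-1. Nothing in the plan aligns the two.

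The first sheet has a second problem. If the wean starts in the morning and the visit follows a few hours later, the chart window ended before any opioid was reduced. Its contents are still tallied as signs of a weaning episode.

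The timing matters clinically. Section 2 (Risk factors) notes that "The onset of withdrawal symptoms can occur within 12 hours following opioid discontinuation", although that sentence concerns discontinuation and not a 10% reduction. The primary result is the frequency of each sign by withdrawal status, intended as groundwork for a bedside screening tool. Signs placed on the wrong day, or recorded before the exposure, go directly into that result.

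**Working it through.** **1. Reproduce the 24 h window.** Each midnight in footnote a could mean the start or the end of the named day. Set 00:00 on visit day D as hour 0.

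- Start / start: -24 to 0, length 24 h (day D-1)
- End / end: 0 to 24, length 24 h (day D)
- Start / end: -24 to 24, length 48 h
- End / start: 0 to 0, length 0 h

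Only the two consistent readings give 24 h. Footnote c's ward window runs forward from midnight of the current day to the visit, so midnight is the start of the day, which selects day D-1. The end/end reading would also need 10–14 h of charting that does not yet exist at the visit.

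**2. Gap to the visit.** The window closes at hour 0 and the visit falls at hour 10 to 14. The newest chart entry is therefore at least 10–14 h old, and the oldest is 24 + 10 = 34 h to 24 + 14 = 38 h old.

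**3. Which signs are affected** (count of Appendix III).

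- Window only, 14: agitation (in ICU), anxiety, fever, hallucinations, seizure, pupil size, hypertension, tachycardia, suction, dyspnea, diarrhea, feeding intolerance, nausea, vomiting.
- Window or visit, 12: tremor, yawning, lacrimation, rhinorrhea, sneezing, mottling, piloerection, sweating, aches, cramps, muscle tone, uncoordinated movement.
- Not this window, 4: startle and time to regain calm (visit only), sleep (10pm to 6am), dysphoria (from the DSM-5 itself).

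14 + 12 + 4 = 30. Fever, nausea, vomiting and pupil size, all window-only, correspond to DSM-5 criterion B items in Appendix IV.

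**4. First sheet.** Let the wean start at hour T of a day and the visit be at hour v. Assume T uniform over 24 h and immediate recognition.

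- T ≤ v: the first visit is the same day, the window is the day before, and the pre-wean share is 100%.
- T > v: the first visit is the next day, the window is the wean day, and the pre-wean share is T/24.

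P(wholly pre-wean) = v/24: 10/24 = 42%, 12/24 = 50%, 14/24 = 58%.

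Mean share = v/24 + (24² − v²)/(2 × 24²):

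- v = 10: 0.417 + 476/1152 = 0.83
- v = 12: 0.500 + 432/1152 = 0.88
- v = 14: 0.583 + 380/1152 = 0.91

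**5. Recognition lag.** Section 4.3.1 judges a wean over 4 h (infusions) or 12 h (intermittent dosing). Taking these as possible lags (an assumption), with visits at 10:00 to 14:00:

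| Lag | Wholly pre-wean, footnote a | Mean pre-wean share, footnote a | Mean pre-wean share, 24 h ending at the visit |
|---|---|---|---|
| 0 h | 42–58% | 83–91% | 50% |
| 4 h | 25–42% | 72–83% | 35% |
| 12 h | 0–8% | 42–58% | 13% |

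If wean starts are instead uniform over 07:00–17:00, the footnote a mean is 69–89% with no lag and 50% with a 12 h lag.

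The last column shows that moving the end of the window closes the 10–14 h gap but does not by itself remove the pre-wean hours.

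**The case against.** The fixed frame is deliberate, has a stated reason, and feeds an analysis that section 6.2 calls predominantly descriptive. That is fair, but standardization does not require a window that stops before the labelled day. Footnote c already carries the window to the evaluation on two other kinds of day.

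Four stronger readings might be inferred, and the documents do not support them.

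- *Every label is paired with the previous day's signs.* This is fully true for 14 signs only. The 12 mixed signs have a same-visit route and 4 lie outside the window. Even within the 14, the yes/no diarrhea item uses slightly different wording for its period.
- *The whole first sheet is pre-wean.* This can apply only to its chart-window entries, and how often it does so depends on prompt recognition of the wean.
- *True signs are undercounted on positive days and the W+/W- contrast is pulled toward zero.* The DSM-5 look-back is not stated, and criterion B admits signs that develop over minutes to several days, so a rating on day D may rest partly on day D-1. Section 5.1.1 also assigns W+ and W- per patient. A sign moved to a DSM-5-negative next-day sheet still belongs to a W+ patient. If all of that patient's sheets are tallied, much of the shift stays within the group. Whether they are all tallied is not clear.
- *Dysphoria looks specific because it is same-day.* Dysphoria is taken from the evaluation that sets the label, so any apparent specificity reflects incorporation, not timing.

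The window's closing time, the missing alignment rule and the pre-wean entries all survive these objections.

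**Conclusion.** The point holds in limited form. Followed as written, footnote a takes 14 of 30 signs at ordinary ICU visits from the calendar day before the DSM-5-labelled day. It closes their window 10–14 h before the visit. This part needs no assumption beyond reading footnote a together with footnote c. It is a rule that misplaces data, not a detail left unsaid.

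When a wean starts on the visit day before the visit, the first sheet's chart-window entries are wholly pre-wean, which conflicts with section 4.4.1. How often this happens rests on assumptions about wean timing and recognition: 42–58% of first windows with uniform starts and no lag, 0–8% with a 12 h lag. The corresponding mean pre-wean shares are 83–91% and 42–58%.

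The direction and size of any net bias in the W+/W- comparison cannot be determined from the documents. The feasibility-based sample size is unaffected.

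**What to change.** - In footnote a, define the ordinary ICU window as the 24 h ending at the evaluation.
- State the same look-back for the DSM-5 rating and record its clock time.
- Start the first window of each weaning episode no earlier than the recorded wean start. Report earlier chart entries separately as pre-wean, so that footnote a, section 4.4.1 and section 5.1.1 agree.

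Do not substitute the full 00:00–24:00 of the visit day. For a rating made around the visit, that would credit it with 10–14 h of signs charted afterwards. It would also depend on a next-day sheet, which may not exist because section 4.5 pauses evaluations when the dose is re-increased.

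The cost is small: changes to one footnote, the DSM-5 form and section 5.1.1. The window will no longer match calendar-day chart totals. First windows will be shorter than 24 h, so counts such as suctioning or bowel movements on those sheets need their window length stated.

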Identifying IWS can be challenging in the critically ill. Several confounding factors (delirium, worsening of critical illness, presence of multiple agents with potential to cause withdrawal, comorbidities) may mimic symptoms similar to opioid or benzodiazepine withdrawal (6, 11). To our knowledge, no study on the symptomatology of IWS has been conducted to describe opioid or benzodiazepine withdrawal exclusively. This is most likely due to the presentation similarities of both syndromes and frequent concomitant use of these drugs in the ICU setting (4, 9).

No physiological markers have been identified to correlate with IWS. In outpatients with chronic opioid addiction, several studies have shown a significant association between increased cortisol and catecholamine levels and acute withdrawal following naloxone reversal. Cortisol and catecholamines are two stress markers that reflect the state of distress and adrenergic hyperstimulation characteristic of opioid withdrawal (12).

To date, the clinical presentation of opioid withdrawal in the adult ICU has not been characterized in a prospective setting. The present study thus aims to describe the symptomatology of opioid-associated iatrogenic withdrawal in two adult tertiary care centers in Montréal, Québec, Canada and explore the potential of using serum cortisol as a biomarker (4, 9).

2. Literature review

Research strategy can be found in Appendix I.

Epidemiology

A systematic review on the epidemiology, risk factors and symptomatology of IWS was recently conducted and identified only one prospective study on IWS in the adult ICU population, which reported an incidence of 16.7% (8, 9). In retrospective trials, incidence ranged from 19.7 to 100% (9). These heterogeneous results are likely attributed to the lack of standardized definition and evaluation of IWS (9).

Risk factors

There is significant overlap in the IWS risk factors identified in pediatric and adult populations such as younger age (3, 4, 7, 9) duration of continuous opioid therapy (i.e. more than three to five days) and prolonged benzodiazepine exposure (4, 5, 7, 9, 13-17). Additional risk factors identified specifically in the adult ICU include higher daily doses of opioids and benzodiazepines, as well as the presence of acute respiratory distress syndrome (ARDS) (7, 9). In the PICU, prolonged exposure prior to weaning

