4.3 Subject selection mode

4.3.1 Inclusion criteria

- Patients 18 years of age or older
- Admitted to the RVH and MGH intensive care units from February to October 2018
- Patients requiring mechanical ventilation and receiving continuous or regular intermittent opioids for at least 72 hours (calculated from the hour of administration of the first opioid dose)
 - o Recent prospective observational studies in the PICU and adult ICU populations have demonstrated that iatrogenic withdrawal symptoms may develop following 3-5 days of continuous opioid therapy (5, 8)
 - o Patient will be considered as receiving regular intermittent opioids if more than half of the scheduled "as-needed" doses within 24 hours were administered.
 - In the event that only prn narcotics are prescribed on a q1h prn or q2h prn basis, patients will be eligible if ≥ 4 prn doses are required per day.
- Weaning of at least 10% from previous stable opioid dose
 - o A weaning episode is defined as a $\geq 10\%$ decrease in the total stable opioid dose received over 4 hours for opioid infusions and over 12 hours for intermittent opioid administration (22)
 - o According to our previous experience (i.e. WAAICUP-1), the weaning definition of $\geq 10\%$ was chosen for practical reasons (8)

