4.3.2 Exclusion criteria

- Patient for whom consent cannot be obtained
- Patient and/or family unable to communicate in French or English
 - o May interfere with obtaining informed consent and OIWS assessment
- Patient who is deaf without appropriate hearing aid
 - o Hearing impairment may interfere with patient communication and assessment of signs and symptoms
- Imminent and predictable death (< 72 hours) according to medical team
- Patients receiving opioids for the purposes of palliative care or prescribed by the palliative care team.
- Severe brain injury, defined as Glasgow Coma Scale (GCS) score of 8 or less at ICU admission
- Moderate brain injury, defined as GCS between 9 and 12, with elevated intracranial pressure (ICP > 20 mmHg) which requires ICP monitoring and osmotherapy
 - o Major confounding factors for withdrawal syndrome by causing shivering, sympathetic drive and autonomic disorders
- Acute neurological condition (e.g. status epilepticus, encephalopathy, stroke)
 - o Potential confounders of OIWS assessment

- If the acute neurological condition resolves within 72 hours, the patient may be included in the study
- Substance abuse prior to ICU admission
 - Chronic alcohol use defined as alcohol consumption of more than 2 drinks/day and/or more than 14 drinks/week for men and 9 drinks/week for women (44)
 - Chronic use of illicit drugs and amphetamines (except amphetamines taken for therapeutic purposes) defined as a consumption of at least 3 times per week
 - Chronic use of opioids (e.g. transdermal fentanyl, methadone, hydromorphone, etc.) defined as a consumption of at least 3 times per week
 - May induce withdrawal and confound OIWS assessment (45)
 - Chronic consumption of these substances will be confirmed by the patient, family, or medical chart
- Admission to the ICU with substance overdose or alcohol withdrawal syndrome.
- Readmission to the MGH or RVH ICU during the recruitment period (limit of one study entry per patient)
- Spinal cord injury above the lumbar region
 - Sympathetic response to withdrawal absent depending on site/level of injury
 - Assessment tools not validated in these patients (DSM-5, RASS, CAM-ICU, CPOT)
- Opioid tolerance prior to ICU admission, defined as regular daily use of opioids for a chronic medical condition or continuous opioid administration for > 7 days prior to ICU admission (46)
Does not include patients who take opioids infrequently.

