4.4 Definition of variables

4.4.1 Primary outcome variables

Dependent variables

- Presence of signs and symptoms of OIWS
 - According to daily evaluation by investigator after an episode of opioid weaning has begun (See Appendix III)

Independent variables

- **Presence of OIWS** (qualitative nominal - dichotomous)
 - According to DSM-5 evaluation completed daily by physician after an episode of opioid weaning has begun
- **Demographic and clinical variables**
 - **Age** (quantitative continuous): Age in years at ICU admission
 - **Sex** (qualitative nominal - dichotomous)
 - **Weight** (quantitative continuous): Weight in kg at ICU admission
 - **Height** (quantitative continuous): Height in cm at ICU admission
 - **Body mass index (BMI)** (quantitative continuous): In kg/m² at ICU admission
 - **Ethnicity** (qualitative nominal)
 - **Site of ICU admission** (qualitative nominal - dichotomous)
 - **Smoking status** (qualitative nominal - dichotomous)
 - Number of cigarettes per day according to medical chart, patient or family at ICU admission (quantitative discrete)
 - Number of pack-years according to medical chart, patient or family at ICU admission (quantitative continuous)
 - **Principal diagnosis at ICU admission** (qualitative nominal)
 - Definite diagnosis according to medical chart at ICU admission using ICD-10 classification
 - **Length of stay in the ICU** (quantitative continuous)
 - Time in hours from ICU admission to ICU discharge, transfer to ward or patient death, according to medical chart
 - Opioid withdrawal has been associated with longer ICU stays (4-6)
 - **Duration of mechanical ventilation** (quantitative continuous)

- Time in hours according to medical chart
- Longer duration of mechanical ventilation has been associated with increased risk of IWS in ICU patients (7)
- **Acute Physiology and Chronic Health Evaluation II Score (APACHE II)** (qualitative ordinal)
 - To assess severity of disease and ICU mortality on a scale of 0 to 71 (47)
 - As reported by an archivist based on data from the first 24 hours of ICU admission
- **Glasgow Coma Scale (GCS)** (qualitative ordinal)
 - To assess mental status and severity of brain injury on a scale of 3 to 15 (48)
 - As reported by nurse on patient flow sheet at ICU admission
- **Renal function**
 - Daily serum creatinine in $\mu\text{mol/L}$ according to medical chart (quantitative continuous)

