 - Presence of renal replacement therapy according to medical chart (qualitative nominal - dichotomous)
 - Drug accumulation may occur when renal excretion is decreased, minimizing OIWS
- **Level of hepatic dysfunction upon ICU admission**
 - Severity of hepatic dysfunction as calculated by the Child-Turcotte-Pugh score at ICU admission (qualitative ordinal)
 - Drug accumulation may occur when hepatic metabolism is decreased
- **Presence of ECMO** (qualitative nominal - dichotomous)
 - Collected daily according to medical chart
 - Patients on ECMO may require higher fentanyl doses due to sequestration of lipophilic drugs and increased volume of distribution (49)
- **Cumulative opioid dose preweaning** (quantitative continuous)
 - Cumulative opioid dose in fentanyl equivalents ($\mu\text{g/kg}$) according to medication administration record (MAR) from time of start of opioids during ICU admission
 - Higher cumulative opioid doses have been associated with increased risk of IWS in ICU patients (8)
- **Duration of continuous opioid administration preweaning** (quantitative continuous)
 - Time in hours according to MAR or patient flow sheet
 - Prolonged opioid exposure has been associated with an increased risk of IWS in ICU patients (4, 8, 13-15)
- **Rate of opioid weaning > 10% from previous stable dose** (quantitative continuous)
 - Calculated in % according to MAR or patient flow sheet
 - Continuous infusion: perfusion rate over previous 4h
 - Continuous intermittent administration: total dose over previous 12h
 - Rapid tapering or abrupt discontinuation of opioids has been associated with increased risk of IWS in ICU patients (7, 20)
- **Presence of clonidine, beta-blockers or antidepressants prior to ICU admission** (qualitative nominal - dichotomous)
 - The agent and whether it was prescribed in ICU will be noted according to the medication reconciliation chart at admission
 - These medications may cause withdrawal when discontinued
- **Occasional use of prescribed opioids prior to ICU admission** (qualitative nominal - dichotomous)
 - Agent (qualitative nominal) and daily doses in fentanyl equivalents ($\mu\text{g/kg/day}$) (quantitative continuous) will be noted according to medication reconciliation chart at admission
 - Chronic opioid users are excluded from the present study (as indicated in exclusion criteria)

- **Prior history of substance abuse** (qualitative nominal - dichotomous)

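### Appendix IV asks for weeks of opioid use or an antagonist, section 4.3.1 enrols from 72 hours, and no visible text says how criterion A is scored

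*Combined protocol and SAP*

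**What the plan says.** **Entry.** Section 4.3.1 takes ventilated patients "receiving continuous or regular intermittent opioids for at least 72 hours", on the ground that "iatrogenic withdrawal symptoms may develop following 3-5 days of continuous opioid therapy". The risk-factor paragraph of section 2 gives a similar window: "duration of continuous opioid therapy (i.e. more than three to five days"). Section 4.3.2 excludes chronic opioid users and patients with "continuous opioid administration for > 7 days prior to ICU admission".

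**Case definition.** Section 4.4.1 sets the presence of OIWS "According to DSM-5 evaluation completed daily by physician after an episode of opioid weaning has begun". Appendix IV is the only visible place where the criteria are listed. Criterion A has two routes: "Cessation of (or reduction in) opioid use that has been heavy and prolonged (i.e., several weeks or longer"), or "Administration of an opioid antagonist after a period of opioid use". No footnote or waiver for the ICU is attached.

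**Use of the rating.** Section 5.1.1 turns each daily DSM-5 result into a withdrawal or no-withdrawal episode. One positive day puts the patient in W+; a patient with none goes to W-. Section 5.1.2 compares cortisol by the same status and computes kappa on the same rating.

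**Nearest caveats.** Section 4.6 concedes that the tool is not validated in the ICU. Section 6.1 defends it because it standardises the physicians' evaluation. Neither these sections nor the limitations in 6.2 mention criterion A or length of exposure.

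**The concern.** The entry rule is built to capture withdrawal after days of exposure. Read literally, the reference standard does not recognise withdrawal after days of exposure unless an antagonist was given. The exclusions in 4.3.2 also remove many of the patients who would already meet the weeks-long requirement on arrival.

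The primary objective is to describe the signs and symptoms of W+ patients. Under literal scoring, short-exposure patients with the full clinical picture leave that group, and all their episodes are tallied in W-. The symptom contrast is then blurred from both sides, and the cortisol contrast with it. That the analysis is mainly descriptive does not help, because what is being described is the W+ group.

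If some physicians waive criterion A and others do not, status depends partly on who rated that day. Kappa would pick up mixed handling only in the dual ratings. If both raters apply the criterion literally they agree, and kappa shows nothing.

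**Working it through.** The plan has no figure of its own to reproduce on this point: the target of 50 in section 5.2 is a feasibility count. The check is therefore a comparison of durations, followed by an illustration.

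**Step 1. Durations.**
- Entry threshold (4.3.1): 72 h = 3 days = 3/7 = 0.43 week.
- Upper end of the stated rationale (4.3.1): 5 days = 5/7 = 0.71 week.
- Criterion A, first route (Appendix IV): several weeks or longer.

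The entry threshold and the whole 3-5 day window are under one week, so they fall short of any reading of several weeks.

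**Step 2. How far exposure can run for the shortest-exposed patient.** Take a patient with no opioids before the ICU, first weaned at 72 h. Time since first dose is 3 + t days, where t is days since first weaning.
- First rating, t = 0: 3 days.
- End of ICU follow-up (4.5), t = 14: 17 days, or 17/7 = 2.4 weeks.
- Latest possible ward visit (4.5), transfer on day 14 plus 96 h, t = 18: 21 days, or 3 weeks.

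If several weeks means 14 days (assumption), this patient could meet the first route only from t = 11. If it means 21 days (assumption), only at the latest ward visit. Both require that days at a reduced dose count as exposure. Opioids before the ICU would lengthen these figures. The 7-day limit in 4.3.2 is worded for continuous administration, so I do not treat it as a cap on all earlier exposure.

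**Step 3. Illustration of size.** Inputs: N = 50 (5.2); incidence 16.7% (section 1, one earlier adult study). Assume 16.7% is the incidence without the duration requirement, and that no patient receives an antagonist.

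Cases C = 50 × 0.167 = 8.35. Let s be the share of cases that meet the first route. Literal W+ = C × s; cases moved to W- = C − W+; their share of W- = moved / (50 − W+).

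| s (assumed) | Literal W+ | Moved to W- | Share of W- |
|---|---|---|---|
| 0.10 | 0.8 | 7.5 | 15.3% |
| 0.25 | 2.1 | 6.3 | 13.1% |
| 0.50 | 4.2 | 4.2 | 9.1% |
| 0.75 | 6.3 | 2.1 | 4.8% |

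Section 4.4.1 says that "Prolonged opioid exposure has been associated with an increased risk of IWS in ICU patients", so long-exposure patients may be over-represented among cases. If a fraction q of patients has weeks of exposure and their risk is R times that of the others, then s = Rq / (Rq + 1 − q).
- R = 1: q = 0.1, 0.2, 0.5 gives W+ = 0.8, 1.7, 4.2.
- R = 3 (assumption): s = 0.25, 0.43, 0.75, so W+ = 2.1, 3.6, 6.3.

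Across these assumptions, literal scoring leaves about 1 to 6 of about 8 cases in W+. These are patients; the primary result in 5.1.1 is per episode, and the documents do not allow that conversion.

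**The case against.** The strongest reply is that nobody means criterion A to be read this way. Section 4.5 calls the physician once a weaning episode is identified, which suggests that entry plus weaning was meant to satisfy it. Appendix IV is a referenced reprint, like the other appendices, and is not shown to be the scoring form. The Appendix II figure and the DSM-5 forms are not visible, so a scoring rule could sit there. This stands as a limit: a reader might infer that literal enforcement will occur, and the documents do not show that. It does not remove the point, because an intent that raters must guess is not the standardisation that 6.1 relies on.

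Second, 5.1.1 resolves a discordant dual rating to positive. That rescues a case on a dual-rated day if at least one rater waives criterion A. It does nothing when both apply it, or on days with a single rater.

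Third, the choice of tool is partly disclosed in 4.6, and pre-weaning duration is already collected, so results can be shown by exposure. Both are true, but the disclosure is general, and exposure alone cannot reveal how a rater treated criterion A.

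Fourth, the illustration is soft. The shares and the risk ratio have no source in the documents. If the earlier study did enforce the duration requirement, 16.7% is already a literal count and the modelled loss disappears. I accept this, and the point does not rest on the illustration.

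**Conclusion.** The conflict between 4.3.1 and Appendix IV is on the page and no visible passage reconciles it. Followed as printed, the criterion codes short-exposure patients who meet B, C and D, and who receive no antagonist, as W-. Waived informally, it leaves the case definition to the individual rater. Either way the primary and cortisol comparisons rest on an unsettled definition, so this should be fixed before rating. Confidence is high for the textual conflict and moderate for actual misclassification.

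Three stronger readings are tempting and not supported:
- That the study cannot produce W+ patients. The 72 hours is a floor, pre-weaning duration is not capped, and the antagonist route remains, so longer-exposed patients can qualify.
- That a known number of cases will be lost. The range of about 1 to 6 remaining from about 8 rests on an outside incidence and on assumed exposure shares, and serves only to show that each case matters in a group this small.
- That Appendix IV is DSM-5 word for word. The source is not available here; what can be said is that no study adaptation is shown.

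**What to change.** Before rating starts, reconcile 4.3.1 with Appendix IV by stating, in 4.4.1 and in Appendix IV, how criterion A is scored for the research case definition. One option is to take it as met by the protocol's own entry and weaning criteria, with physicians rating B, C and D. If it is adapted:
- call the reference *modified DSM-5* throughout;
- record the literal answer to criterion A as a separate yes/no item;
- tabulate W+ and W- by that item as a descriptive check, beside the pre-weaning opioid duration already collected under 4.4.1.

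If a rule already exists on the forms or in the Appendix II figure, it should be brought into the text.

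The cost is one sentence in two places, one form item and one table. Visits and sample size do not change. The downsides are that the reference would no longer be unadapted DSM-5, and that the literal W+ group may be too small for the table to show more than counts.
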